7.13. Subgroup Analyses

General subgroup analyses are described in the CPMP SAP Version 5.

Study OA05 will also consider the subgroup analyses for the primary efficacy outcome and key secondary outcome (see [Table OA05.7.3](#)).

Table OA05.7.3. Subgroup Analyses for Primary Outcome and Key Secondary Outcome

Subgroup Variable	Categories
Kellgren-Lawrence Grade	Categories: Grade 2, Grade 3, and Grade 4 Note: Alternative groupings may be created based on the number of participants classified within each grade (for example, <3, ≥ 3)

The subgroup analyses will be conducted using similar modeling approaches as the primary and key secondary analyses. Additional factors in the model are described in the CPMP SAP Version 5. The treatment difference at the endpoint will be reported within each level of the subgroup factor along with 95% credible intervals. Frequentist MMRM may be performed as a sensitivity analysis using the modeling approach described in the CPMP SAP Version 5.

7.14. Protocol Deviations

Participants with study important protocol deviations will be summarized by type of deviation and listed by treatment and investigative site.

[figure not shown]
Important protocol deviations for the study are described in the CPMP and Study OA05 Trial Issue Management Plans.

7.15. Interim Analyses and Data Monitoring

Safety review will be conducted under the auspices of an Assessment Committee according to the specifications set forth in the protocol. These analyses will be at the CPMP level and will consider data from all ongoing ISAs. Details are provided in the CPMP SAP Version 5. No interim analyses are planned for Study OA05. Unplanned interim analyses may be conducted for reasons including futility analyses, early efficacy analyses, safety analyses, or other analyses, if deemed needed for key business decisions and planning.

[figure not shown]
7.16. Planned Exploratory Analyses

The following analyses may be conducted for exploratory purposes:

7.17. Totality of Evidence for Efficacy

The totality of evidence analysis approach for efficacy data has been briefly described in the CPMP SAP Version 5. A multivariate Bayesian model will be fit within each ISA to assess efficacy ToE across domains. To inform the aggregation of model-based estimates for domain scores, important weights for each scale within a domain are described in [Table OA05.7.4](#).

The text 'CCI' is displayed in a large, bold, red font. It is positioned on a solid black rectangular background. The letters are slightly shadowed, giving them a 3D appearance.

7.18. Totality of Evidence for Safety

The totality of evidence analysis approach for safety data has been briefly described in the CPMP SAP Version 5. The key safety events to be considered for Study OA05 are listed below by domain:

General AE Information

- Serious AEs including death related to study treatment
- Study discontinuation due to AE
- Treatment discontinuation due to AE.

Cardiovascular

- QTcF prolongation: >60 msec increase or QTcF >500 msec
- Serious cardiac disorders AE.

Liver function

- Drug-induced liver injury: at least 1 of the following 2 conditions:

The text 'CCI' is displayed in a large, bold, red font. It is positioned on a solid black rectangular background. The letters are slightly shadowed, giving them a 3D appearance.

Metabolic function

- Serious hypoglycemia AE
- Serious hyperglycemia AE
- Treatment-emergent hemoglobin A1c: Shift from low/normal at baseline to high at least once.

Renal function

- Treatment-emergent abnormal eGFR: Shifts
 - Mild at baseline to moderate/severe
 - Moderate at baseline to severe.

Neurologic function

- Treatment-emergent abnormal shift on the overall neurologic assessment
- Serious neurologic events
- Seizures FMQ both narrow and broad terms.

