5.2. Exclusion Criteria

Participants are excluded from the study if any of the following criteria apply:

- [1077] Have an eGFR of <30 mL/min/1.73 m², based on the Chronic Kidney Disease Epidemiology Collaboration formula at Visit 1 or Visit 2.
- [1078] Have known allergies to LY3857210, related compounds or any components of the formulation, or history of significant atopy.
- [1079] Women who are pregnant or breastfeeding.

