7.12.5. Clinical Laboratory Evaluation

The general analysis of laboratory parameters is described in the CPMP SAP Version 5.

In this ISA, laboratory results will be reported for the entire 10-week study period. Study OA05 will also consider the following analyses of lab analytes used to assess renal function. The planned summaries for these analytes are the same as those that have been described in the Study

CPMP SAP Version 5; however, the reporting of these analytes will be separate from the general analysis of laboratory parameters.

- Renal data analyses:
 - Serum creatinine (change from baseline in mg/dL)
 - eGFR; Chronic Kidney Disease Epidemiology Collaboration (algorithm using serum creatinine) Algorithm: Provided by central laboratory
 - For eGFR calculation, we will summarize shift tables of eGFR changes for baseline versus postbaseline by minimum, maximum, and last observed eGFR result:
 - Category 1: Normal or increase in GFR (≥ 90 mL/min/1.73m²)
 - Category 2: Mild reduction in GFR (60 to 89 mL/min/1.73m²)
 - Category 3a: Moderate (a) reduction in GFR (45 to 59 mL/min/1.73m²)
 - Category 3b: Moderate (b) reduction in GFR (30 to 44 mL/min/1.73m²)
 - Category 4: Severe reduction in GFR (15 to 29 mL/min/1.73m²)
 - Category 5: Kidney failure (GFR <15 mL/min/1.73m² or dialysis).

Abnormal eGFR is specified below and will be summarized in the laboratory summary tables.

- Abnormal low: <90 mL/min/1.73m²
- Abnormal high: As specified by central laboratory.

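### The renal event in the safety totality-of-evidence list (SAP 7.18) cannot occur in a participant whose baseline eGFR is normal

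*SAP*

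**What the plan says.** SAP 7.18 lists by domain the key safety events for the OA05 totality-of-evidence summary. The renal domain holds one event, treatment-emergent abnormal eGFR, with two qualifying shifts: "Mild at baseline to moderate/severe" and "Moderate at baseline to severe". No redaction mark appears in that block.

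SAP 7.12.5 supplies the only eGFR scale in the SAP. It starts at "Category 1: Normal or increase in GFR" (90 mL/min/1.73m² or above) and runs through mild (60 to 89), moderate 3a (45 to 59), moderate 3b (30 to 44) and severe (15 to 29) to "Category 5: Kidney failure" (below 15, or dialysis). The same section flags eGFR as "Abnormal low: <90 mL/min" (per 1.73m²) and plans shift tables of baseline against post-baseline categories "by minimum, maximum, and last observed eGFR result".

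The HbA1c event, also in SAP 7.18, is defined as "Shift from low/normal at baseline to high at least once".

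Protocol 5.2, criterion [1077], excludes people who "Have an eGFR of <30 mL/min/1.73 m²" at Visit 1 or Visit 2. It sets no upper limit.

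**The concern.** Someone who starts with normal kidney function and loses much of it during treatment is a clear case for a treatment-emergent renal event. The 7.18 definition shuts that case out. Only participants already below 90 at baseline can have the event, so the normal-baseline group contributes zero by construction. A reader of the summary could take that zero as an observation.

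Two consequences follow. The renal event count is incomplete, and it depends on the baseline eGFR mix of the participants enrolled. The domain also has no second item to catch the missed cases. The cardiovascular, metabolic and neurologic domains each include a serious adverse event item; the renal domain does not.

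**Working it through.** The plan states no figure for this event, so there is none to reproduce. The check applies the two listed shifts to the categories in 7.12.5.

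**Inputs**
- Categories and bounds: SAP 7.12.5. SAP 7.18 does not restate cut-offs, so using these bounds is an assumption. The words mild, moderate and severe match.
- Qualifying shifts: SAP 7.18.
- Eligible baselines: Protocol 5.2 excludes eGFR below 30, which leaves normal, mild and moderate.

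**Step 1: shifts ending in moderate or worse, with 3a and 3b pooled**

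| Baseline | Possible worse end categories | Counted if 'severe' is Category 4 only | Counted if 'severe' includes Category 5 |
|---|---|---|---|
| Normal (90 or above) | moderate, severe, failure: 3 | 0 | 0 |
| Mild (60 to 89) | moderate, severe, failure: 3 | 2 | 3 |
| Moderate (30 to 59) | severe, failure: 2 | 1 | 2 |
| Total | 3 + 3 + 2 = 8 | 3 | 5 |

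From a mild or moderate baseline, 3 of 5 shifts count on the narrow reading and 5 of 5 on the wide one. From a normal baseline, 0 of 3 count on both.

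**Step 2: the same check with all six categories kept separate**

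There are 5 + 4 + 3 + 2 + 1 = 15 worsening pairs. The narrow reading counts 3 (from mild) + 1 (from 3a) + 1 (from 3b) = 5. The wide reading adds failure as an end category for mild, 3a and 3b, which gives 8. From normal it is 0 of 5 both times. The grouping changes the totals but not the result for normal baseline.

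**Step 3: size of fall, as (baseline − post-baseline) / baseline, in whole numbers**

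| Baseline to post-baseline | Fall | Percent | Renal event? |
|---|---|---|---|
| 60 to 59 (smallest fall that counts) | 1 | 1/60 = 1.7% | Yes |
| 65 to 55 | 10 | 10/65 = 15.4% | Yes |
| 89 to 15 | 74 | 74/89 = 83.1% | Yes |
| 90 to 59 (smallest fall from normal to moderate) | 31 | 31/90 = 34.4% | No |
| 95 to 25 | 70 | 70/95 = 73.7% | No |

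The rule does count some large falls. However, every omitted fall from normal to moderate or worse is at least 31 mL/min/1.73m², while a fall of 1 from the bottom of the mild range counts.

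**The case against.** Several points can be made for the plan as written.

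- **The label can be defended in part.** The SAP's abbreviations section lets a treatment-emergent event be either new or a worsening of something already present. Worsening from mild or moderate fits the second limb. That stands, but the first limb, new abnormality, is then missing altogether.
- **Leaving out falls just below 90 may be deliberate.** Small changes around 90 are likely to be noise. That would justify omitting normal to mild, and the fix below keeps that omission. It does not explain omitting normal to moderate or severe.
- **The HbA1c line is not a template.** It is a simple low/normal-to-high shift and omits worsening from a high baseline. This is fair. The comparison shows only that the same list elsewhere allows an event from normal; the finding does not rest on it.
- **The counts are of table cells, not participants.** This is correct. Nothing in the documents says how often a fall of 31 or more from normal would occur in about 125 participants over 8 weeks.
- **The information is not lost, and both arms follow the same rule.** The 7.12.5 shift tables show every omitted case. The General AE items catch treatment-related serious events and discontinuations due to adverse events, though not as renal events. The cost is sensitivity in one summary, not a built-in bias between arms.
- **The master SAP (CPMP SAP Version 5) may say more.** It is not among the documents reviewed. But 7.18 says the approach is only briefly described there and gives the OA05 event list itself.

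These points limit the consequence. None opens the renal event to a participant with normal baseline eGFR.

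**Conclusion.** The concern holds. As written, the renal event in SAP 7.18 is closed to every participant with baseline eGFR of 90 or above, under either reading of 'severe'. This rests on applying the 7.12.5 categories to 7.18, and on the master SAP not adding a shift from normal.

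The omission of kidney failure as an end category is secondary. On the narrow reading, a fall to below 15 counts from no baseline; if 'severe' was meant to include failure, that gap is only one of wording.

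The point should be fixed, but its reach is one safety summary. The effect on any conclusion cannot be stated, because 7.18 gives no weight or threshold for the renal domain.

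**What to change.** In SAP 7.18, define the renal event with the 7.12.5 categories:

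- normal or mild at baseline to moderate, severe or kidney failure;
- moderate at baseline to severe or kidney failure.

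All 8 shifts in Step 1 would then count. In the six-category listing, the total becomes 8 + 4 = 12 of 15. The three left out are normal to mild, 3a to 3b, and severe to failure; the last starts from a baseline that the protocol excludes.

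While editing, it would help to say which post-baseline value defines the shift, unless the master SAP already does. Counting a shift that occurs at least once would match the HbA1c line and the minimum-eGFR shift table in 7.12.5.

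The cost is two lines of SAP text and one derivation from eGFR data already collected and tabulated. The renal event count may rise slightly.

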7.19. Annual Report Analyses

Analyses will be produced as needed for the purposes of providing periodic safety reviews to regulatory agencies (for example, Development Safety Update Reports). Data from this ISA will be combined with data from other clinical studies that investigated LY3857210. In all analyses, a combined LY arm will be created which includes participants assigned to any dose of LY3857210 in the included studies, including LY-combination regimens.

The following data will be summarized by treatment group.

- enrollment (ongoing and completed)
- demographics (race, ethnicity, and gender)
- exposure
 - cumulative number of subjects exposed to LY3857210
 - cumulative number of subjects exposed to LY3857210 by age
 - cumulative number of subjects exposed to LY3857210 by sex
 - cumulative number of subjects exposed to LY3857210 by race
- cumulative summary of serious AEs.

The following listings will be provided.

- list of serious AEs during the reporting period
- list of subjects who died
- cumulative list of subjects who discontinued due to an AE (discontinued from treatment or study)
- list of subjects who discontinued due to an AE during the reporting period.

Additional analyses may be added or omitted at the time of report submission as needed.

7.20. Clinical Trial Registry Analyses

Additional analyses will be performed for the purpose of fulfilling the CTR requirements.

Analyses provided for the CTR requirements include the following:

Summary of AEs, provided as a dataset that will be converted to an XML file. Both “Serious” AEs and “Other” AEs are summarized by treatment group and by MedDRA PT.

- A serious AE is an AE that is considered “Serious” whether or not it is a treatment emergent.
- An AE is considered in the “Other” category if it is both a TEAE and is not serious. For each “Serious” AE and “Other” AE, for each term and treatment group, the following are provided:
 - the number of participants at risk of an event
 - the number of participants who experienced each event term
 - the number of events experienced.
- Consistent with www.ClinicalTrials.gov requirements, “Other” AEs that occur in fewer than 5% of participants in every treatment group may not be included if a 5% threshold is chosen (5% is the minimum threshold).
- AE reporting is consistent with other document disclosures for example, the Clinical Study Report and manuscripts.

8. Unblinding Plan

The general unblinding plan is described in the CPMP SAP Version 5 and in the CPMP Blinding and Unblinding Plan Version 2. Unblinding considerations specific to Study OA05 are provided below.

PK/PD Analysis Planning

A limited number of prespecified individuals who are not part of the blinded study team and do not have direct site contact, data entry, or data validation responsibilities, may receive access to unblinded data, prior to an interim or final database lock, to initiate the PK and/or PK/PD model development processes. This will be described in the unblinding plan. Information that may unblind the study during the analyses will not be reported to study sites or blinded study team until the study has been unblinded.

9. References

Bellamy N. The WOMAC Knee and Hip Osteoarthritis Indices: development, validation, globalization and influence on the development of the AUSCAN Hand Osteoarthritis Indices. *Clin Exp Rheumatol.* 2005;23(5 suppl 39):S148-S153.

Signature Page for VV-CLIN-093341 v1.0

Approval	PPD
	27-Jun-2023 15:49:05 GMT+0000

Signature Page for VV-CLIN-093341 v1.0
